8.2. Setting

This study will be set in the three Scandinavian countries, each of which has tax-supported universal health care; routine recording of prescription dispensings, hospital diagnoses, migrations and deaths, and individual-level data linkage, thus enabling nearly complete follow-up of the entire populations and virtually no selection bias in epidemiologic studies.

The source population of this study will be persons who are alive and residents of each Scandinavian country on 01 January 2013. In 2013, the adult population was 4,412,327 persons in Denmark (www.statistikbanken.dk, figure for first quarter 2013); 3,928,378 persons in Norway (<https://www.ssb.no/en/befolkning>) and 7,627,772 persons in Sweden (<http://www.scb.se/>, figure for 31 December 2012).

8.2.1. Study population

The study population will be identified as treatment-naïve adults (aged 18 years or older on the index date) in the source population who have been diagnosed with non-valvular atrial fibrillation and initiated apixaban, rivaroxaban or dabigatran ('the NOACs') or warfarin between 01 January 2013 and 31 December 2016. Warfarin accounts for >98% of the vitamin K antagonists dispensed in the Scandinavian countries (Table 2). In the main analyses, patients will be followed from the index date until a given endpoint, death, OAC switching or discontinuation, emigration, or 31 December 2016, whichever comes first. In the sensitivity analyses of selected contrasts (an intention-to-treat like analysis), patients will be followed from the index date until a given endpoint, death, emigration, or 31 December 2016, whichever comes first.

8.2.2. Inclusion criteria

Patients must meet all of the following inclusion criteria to be eligible for inclusion in the study:

1. Age 18 years or older on the date of initiation of a NOAC or warfarin
2. Initiation of apixaban, dabigatran, rivaroxaban, or warfarin between 01 January 2013 and 31 December 2016 (inclusive); the date of the first dispensing of any of the above agents during the study period will be the index date
3. Diagnosis of AF recorded, using International Classification of Diseases, Tenth Revision (ICD-10) codes, in each country's national patient registry up to 5 years before or up to 60 days after the index date, inclusive

8.2.3. Exclusion criteria

Patients meeting any of the following criteria will be excluded:

[figure not shown]
1. A diagnosis of mitral stenosis AND/OR record of presence of mechanical heart valves identified by ICD-10 or procedure codes up to 5 years before the index date, to rule out non-NVAF indication of OAC use
2. A diagnosis of pulmonary embolism (PE) or deep vein thrombosis (DVT) recorded up to 6 months before and including the index date, to rule out non-NVAF indication of OAC use
3. A record of knee arthroplasty or hip arthroplasty 6 weeks before and including the index date, to rule out non-NVAF indication of OAC use
4. A dispensing, within the 12 months of the index date (the washout period), of any VKAs (Anatomical Therapeutic Chemical (ATC) codes B01AA), direct thrombin inhibitors (ATC codes B01AE), or direct factor Xa inhibitors (ATC codes B01AF)
5. Dispensing of more than one different OACs on the index date

6. Residence in a given country for less than 5 years before the index date
7. A record of pregnancy in a national patient registry within 9 months before index date

After applying the inclusion and exclusion criteria, eligible patients will be assigned to the following exposure cohorts based on the newly initiated OAC, with index date being the date of initiation (Figure 2):

- **Apixaban cohort:** NVAF patients who initiated apixaban on the index date
- **Dabigatran cohort:** NVAF patients who initiated dabigatran on the index date
- **Rivaroxaban cohort:** NVAF patients who initiated rivaroxaban on the index date
- **Warfarin cohort:** NVAF patients who initiated warfarin on the index date

Figure 2. Flow diagram of identification of the study population

Abbreviations: AF atrial fibrillation, DVT deep vein thrombosis, OAC oral anticoagulant, PE pulmonary embolism, VKA vitamin K antagonist

8.3. Variables

8.3.1. Exposure

Initiation of an OAC in each cohort will be measured using outpatient dispensings recorded in the nationwide prescription registries of the three Scandinavian countries (see [Table 1](#) in the section [Data sources](#)).

8.3.2. Endpoints

The following primary and secondary endpoints will be defined.

8.3.2.1. Primary endpoints

- Any stroke (i.e, ischaemic or haemorrhagic stroke) or systemic embolism
- Any bleeding (i.e., intracranial, gastrointestinal, other) at an acute hospitalization with an overnight stay

8.3.2.2. Secondary endpoints

- Ischaemic stroke at an acute hospitalization with an overnight stay
- Haemorrhagic stroke at an acute hospitalization with an overnight stay
- Intracranial bleeding at an acute hospitalization with an overnight stay
- Gastrointestinal bleeding at an acute hospitalization with an overnight stay
- Acute myocardial infarction at an acute hospitalization with an overnight stay
- Systemic embolism at an acute hospitalization with an overnight stay
- Death of all causes
- The composite endpoint of ischemic stroke at an acute hospitalization with an overnight stay, systemic embolism at an acute hospitalization with an overnight stay, acute myocardial infarction at an acute hospitalization with an overnight stay, or all-cause mortality
- Any bleeding at an acute or planned hospitalization with an overnight stay
- Any bleeding occurring at an acute hospital contact without an overnight stay

- Bleeding (intracranial, gastrointestinal, other) recorded as the primary diagnosis at an acute hospitalization with an overnight stay (sensitivity analysis)

8.3.2.3. Exploratory endpoints

Bleeding- and stroke-related acute care hospital care resource utilization among the OAC-treatment naïve NVAf patients who initiate apixaban, dabigatran, rivaroxaban, or warfarin, specifically, the number of hospitalizations and bed days and to assess associated costs to the extent possible.

8.3.3. Covariates

Baseline characteristics of the study cohorts will be ascertained during the maximum of 5-year baseline before and including the index date (38): age at index date (in groups and as a continuous variable), sex, overall comorbidity (using the Charlson Comorbidity Index (39, 40)), the CHA₂DS₂VASc score, CHADS₂ score, the HAS-BLED score, major bleeding, ischemic stroke, transient ischemic attack (TIA), history of heart failure (HF), cancer, diabetes, hypertension, chronic kidney disease, liver disease, myocardial infarction, alcohol abuse, peripheral arterial disease (PAD), coronary artery disease (CAD), dementia, cancer, and cardioversion. Baseline concomitant medication use will be assessed as history of dispensings for angiotensin converting enzyme (ACE) inhibitors, amiodarone, dronedarone, beta-blockers, H₂-receptor antagonists, proton pump inhibitors, antidiabetics, anti-platelets, statins, aspirin, selective serotonin reuptake inhibitors (SSRIs), and non-steroidal anti-inflammatory drugs (NSAIDs). Socioeconomic characteristics will include income, education, and employment. Data on socioeconomic characteristics will be available in Denmark and Sweden.

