8.1. Study design

This study will be a cohort study based on data from national routine population-based administrative health registries and databases in Denmark, Norway, and Sweden. The period

for identifying the study population (identification period) will be from 01 January 2013 to 31 December 2016, to reflect dates of apixaban availability and the years of available data. For each patient included in the study, the date of dispensing of the first OAC during the above period will be the index date (Figure 1).

This study will utilize the ‘active comparator new user’ design (34-36). Restriction of the study population to OAC treatment initiators (new users) emulates the principle of RCTs of aligning the start of follow-up with the start of treatment. This design reduces the risk of selection bias, such as healthy initiator bias, whereby prevalent users of medications may represent a selected group of all users, in that they are depleted of patients who discontinued treatment after experiencing an adverse event (AE) shortly after initiation (‘depletion of susceptibles’) (37). Depletion of susceptibles is avoided by the new user design. Propensity-score matched contrasts will be estimated for each NOAC vs. warfarin, to allow comparison of results with those from RCTs.

Figure 1. Study design schema

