8.3.4. Subgroups

Consistency for the primary endpoints and of the composite secondary endpoint will be evaluated among patients according to the following clinical or demographic characteristics:

- In each country (Denmark, Norway, Sweden)
- By age at OAC initiation (<65; 65-<75 years, ≥75-<85 years; and in patients ≥85 years if sample size permits)
- By sex (men and women)
- According to CHA₂DS₂VASc score category in the baseline
- According to CHADS₂ score category in the baseline
- According to HAS-BLED score category in the baseline
- According to initial dosage in the baseline (any licensed dose for AF vs reduced dose)
- In patients with/without chronic kidney disease (CKD) in the baseline

- In patients with/ without heart failure (HF) in the baseline
- In patients with/ without coronary artery disease (CAD) in the baseline
- In patients with/ without peripheral arterial disease (PAD) in the baseline
- In patients with/ without prior ischaemic stroke in the baseline
- In patients with/ without prior unspecified stroke in the baseline
- In patients with/ without prior haemorrhagic stroke in the baseline
- In patients with/ without prior TIA in the baseline
- In patients with/without prior systemic embolism at baseline
- In patients with/without prior gastrointestinal bleeding at baseline
- In patients with/without prior intracranial bleeding at baseline
- In patients with/without diabetes in the baseline

Depending on sample size, subgroup analyses for the primary and the composite endpoint may be repeated in some of the above subgroups with appropriate re-matching.

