8.7.2. Main analysis

To compare risks of the endpoints across the study cohorts, time to event analysis will be undertaken, using Cox proportional-hazards regression, with death as competing risk for endpoints not including death. Crude and adjusted HRs and 95% confidence intervals (CI) will be estimated for initiators of each NOAC. Follow-up will end on the date of a given endpoint, date of death (for non-death endpoints), date of discontinuation of or switch from the index OAC, date of emigration, or 31 December 2016, whichever comes first. A patient will be considered on-treatment from the date of the first dispensing of the index OAC and for the subsequent number of days corresponding to the number of tablets in all dispensed packages for rivaroxaban (used once daily) or half the number of tablets in all dispensed packages for dabigatran or apixaban (used twice daily) as long as there are no more than 30 days between the expiration and the start of the two adjacent dispensings. A discontinuation will be recorded as soon as 31 days elapse after the expiration of the number of days in a given dispensing (date of dispensing + days supplied + 31 days) in the absence of the next dispensing of the same OAC.

The approach to calculate the warfarin discontinuation date will be based on the median daily dose for all warfarin patients; this median daily dose will be used to calculate an end of supply date based on the dispensing strength and number of tablets in a package for each patient. Discontinuation will be assumed if there was no warfarin prescription within 30 days of the end date of the supply.

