8.7.3. Sensitivity analysis

The following sensitivity analyses will be performed overall, for the primary endpoints and the composite secondary endpoint:

1. The intention-to-treat (ITT) like analyses: the overall comparative PS-matched analyses of the primary endpoints and the composite secondary endpoint will be repeated whereby patients in each OAC cohort will be followed from the index date until a given endpoint, death, emigration, or study end (no censoring by discontinuation or switching)
2. The overall comparative analyses of the primary endpoints and the composite secondary endpoint in the propensity score (PS)-matched analysis set will be repeated whereby the on-treatment time for patients treated with warfarin will be estimated based on a recently published methods using on maximum likelihood estimation of a parametric two-component mixture model for the waiting time distribution (52, 53). The algorithm found that 80% of current warfarin users will have presented themselves again for a refill after 91 days. A 30-day grace period will be added at the end of the 91 days
3. The overall comparative analyses of the primary endpoints and the composite secondary endpoint will be repeated in the full analysis dataset using conventional adjustment instead of PS matching
4. The overall comparative analyses of the primary endpoints and the composite secondary endpoint will be repeated in the full analysis dataset using conventional adjustment instead of PS matching
5. Analysis stratified on the initial dose will be performed after PS rematching within the initial dose defined strata.

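### The index date lies in both the baseline window and follow-up, with no precedence rule, so a stroke, bleed or myocardial infarction dated that day is both history and endpoint

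*Protocol*

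**What the plan says.** Protocol 8.1 defines time zero: "the date of dispensing of the first OAC during the above period will be the index date". Four statements then place that day in a window.

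- **Baseline (8.3.3):** characteristics are "ascertained during the maximum of 5-year baseline before and including the index date". The list includes major bleeding, ischaemic stroke, myocardial infarction and the CHA₂DS₂VASc and HAS-BLED scores.
- **Main follow-up (8.2.1):** "patients will be followed from the index date until a given endpoint, death, OAC switching or discontinuation, emigration, or 31 December 2016".
- **On-treatment time (8.7.2):** "A patient will be considered on-treatment from the date of the first dispensing of the index OAC".
- **ITT-like analysis (8.7.3):** patients are "followed from the index date until a given endpoint, death, emigration, or study end".

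Section 8.3.4 splits patients by event history, for example "In patients with/without prior gastrointestinal bleeding at baseline", and likewise by prior ischaemic, haemorrhagic or unspecified stroke, TIA, systemic embolism and intracranial bleeding. The primary endpoints are stroke or systemic embolism, and bleeding. Section 7.1 requires an acute overnight hospitalization for both. Acute myocardial infarction is a secondary endpoint and part of the composite.

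Operational definitions and the propensity-score variable list are left to the SAP (8.4, 8.7).

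**The concern.** A baseline window and a risk window should not share a day. Where they do, an event on that day can help set the covariate or subgroup used to analyse it. Dispensing is recorded by date, so an admission on the same day cannot be shown to follow first intake. Some such events may be part of the reason treatment began rather than a consequence of it.

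The protocol itself treats the index date as pre-exposure elsewhere. In 8.2.3, pulmonary embolism, deep vein thrombosis and joint replacement recorded up to and including the index date exclude a patient, because they point to another indication. A stroke or bleed on that same day is nevertheless allowed to count as an outcome.

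Two things are at stake. The first is whether some counted endpoints preceded exposure. The second is whether the consistency analyses in 8.3.4 are distorted when the subgroup is defined by the same type of event as the endpoint.

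**Working it through.** **Step 1: set the windows side by side.** Call the index date day 0. The baseline window is at most 5 years and ends on day 0 inclusive (8.3.3). Main follow-up starts on day 0 (8.2.1), on-treatment time starts at first dispensing, which is day 0 (8.1, 8.7.2), and ITT-like follow-up starts on day 0 (8.7.3). The overlap is exactly one day in both analyses. The exclusion criteria (8.2.3) do not remove patients with a stroke, bleed or infarction on day 0, and no section gives a tie rule.

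**Step 2: find which events sit on both sides.**
- Ischaemic stroke: covariate, subgroup, and part of a primary endpoint.
- Gastrointestinal or intracranial bleeding: subgroup and part of a primary endpoint. Major bleeding is a covariate.
- Haemorrhagic stroke and systemic embolism: subgroup and part of a primary endpoint, but not named individually in the 8.3.3 list.
- Myocardial infarction: covariate, and part of the secondary composite.
- Bleeding at other sites: primary endpoint with no subgroup of its own.

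**Step 3: follow one patient through.** Take an acute overnight admission for gastrointestinal bleeding dated day 0. As written, the patient belongs to the stratum with prior gastrointestinal bleeding and also has the bleeding endpoint at time zero. The stratum without such a history cannot contain a day-0 gastrointestinal bleed.

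**Step 4: size at the background rate.** No figure in the protocol depends on this point, so there is none to reproduce. Section 8.5 supplies 24,000 apixaban patients and a major bleeding risk of 2-3% per year.

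Expected day-0 bleeds = N × annual risk / 365.25:
- 24,000 × 0.02 / 365.25 = 1.3
- 24,000 × 0.03 / 365.25 = 2.0

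Share of first-year events = 1 / 365.25 = 0.27%, whatever the annual rate. Section 8.5 expects only 300 to 400 bleeds in the first year, below 24,000 × 2-3% = 480 to 720. On that basis one day gives 300/365.25 = 0.8 to 400/365.25 = 1.1 bleeds, the same share.

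**Step 5: size if events cluster on day 0.** Assumption, not in the documents: the day-0 rate is k times background. Expected day-0 bleeds are k times the step 4 figures, and their share of first-year events is k / (364.25 + k).
- k = 10: 13 to 20 bleeds, share 10/374.25 = 2.7%
- k = 60: 79 to 118 bleeds, share 60/424.25 = 14.1%

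These values show how the result scales and are not estimates.

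**Step 6: effect on a comparison.** With a true ratio of 1, the apparent first-year ratio is about (364.25 + k₁)/(364.25 + k₀), where k₁ and k₀ are the multiples in the two arms.
- k₁ = k₀: ratio 1.00
- k₁ = 30, k₀ = 10: 394.25/374.25 = 1.05
- k₁ = 10, k₀ = 30: 374.25/394.25 = 0.95

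**Step 7: like-with-like subgroups.** Every day-0 gastrointestinal bleed in the cohort falls in the stratum with that history. Its weight there is the number of day-0 bleeds divided by that stratum's events alone, so the share exceeds the whole-cohort figure for that event type. The protocol gives no stratum sizes, so no number can be attached.

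**The case against.** The strongest reply is that this belongs to the SAP. Section 8.4 refers there for every operational definition, following patients from the index date is the ordinary way to state time zero, and the SAP may well set the event date or begin counting the next day. That stands for event dating and for the propensity-score list. It does not remove the overlap, because the protocol fixes both windows itself. If the SAP starts on day 1, the protocol text still needs aligning.

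A second reply is that every contrast uses the same windows in both arms. This also stands: equal clustering leaves a true ratio of 1 unchanged. However, 8.9 accepts that drug choice may follow characteristics that predict bleeding, so equal clustering cannot be presumed.

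A third reply is that other repairs would do, such as ending baseline the day before. That would make the windows disjoint, but would still count possibly pre-exposure events as outcomes.

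The text also invites some stronger readings that the documents do not support:

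- **That day-0 events are a sizeable share of all endpoints.** Nothing in the protocol anchors such a figure. If events are dated by admission, a bleed treated before discharge and dispensing falls before day 0. If dated by discharge, it could fall on day 0. The protocol does not say which applies.
- **That day-0 events can never enter any stratum without prior events.** This holds only for the same event type. A day-0 gastrointestinal bleed can be without prior stroke or intracranial bleeding, and a bleed at another site can be without both named bleeding histories.
- **That the event is certainly a matching variable.** This is likely, since these are listed covariates and adjustment is by propensity-score matching, but the variable list is in the SAP.

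**Conclusion.** The overlap is real and rests on the protocol's own wording. Day 0 belongs to baseline and to follow-up, with no precedence rule, so a qualifying event that day counts twice and may not follow exposure.

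Its size cannot be estimated from the documents. At the background rate in 8.5 it is about 1.3 to 2.0 bleeds in 24,000 patients, about 0.3% of first-year events, which would not matter. It becomes material only if events cluster on the dispensing day. The hazard ratio is then biased only if the clustering differs by drug: 30 against 10 times background, both assumed, moves a true ratio of 1 to about 1.05 or 0.95. A reader might infer that the main hazard ratios are biased, but the documents do not show differential clustering. The prior-event subgroups of the same event type are most exposed. The correction is worth making because it is cheap and lets readers see whether the day matters.

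**What to change.** Amend 8.2.1, 8.7.2 and 8.7.3 together:

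1. Keep the baseline window through the index date.
2. Start ascertainment of non-fatal endpoints and time at risk on the following day, in all cohorts and in both the on-treatment and ITT-like analyses.
3. State whether the admission or the discharge date dates an event.
4. State how deaths on the index date are handled. Death is a secondary endpoint and part of the composite, and it also ends follow-up for the other endpoints.
5. Report index-date strokes, bleeds, infarctions and deaths descriptively by cohort.

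The cost is a few lines of text and no new data. A few true same-day events leave the comparison, but they remain visible in the descriptive report. The start of follow-up shifts by one day for every cohort alike, so it stays tied to treatment start as 8.1 intends.

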8.3.4. Subgroups

Consistency for the primary endpoints and of the composite secondary endpoint will be evaluated among patients according to the following clinical or demographic characteristics:

- In each country (Denmark, Norway, Sweden)
- By age at OAC initiation (<65; 65-<75 years, ≥75-<85 years; and in patients ≥85 years if sample size permits)
- By sex (men and women)
- According to CHA₂DS₂VASc score category in the baseline
- According to CHADS₂ score category in the baseline
- According to HAS-BLED score category in the baseline
- According to initial dosage in the baseline (any licensed dose for AF vs reduced dose)
- In patients with/without chronic kidney disease (CKD) in the baseline

- In patients with/ without heart failure (HF) in the baseline
- In patients with/ without coronary artery disease (CAD) in the baseline
- In patients with/ without peripheral arterial disease (PAD) in the baseline
- In patients with/ without prior ischaemic stroke in the baseline
- In patients with/ without prior unspecified stroke in the baseline
- In patients with/ without prior haemorrhagic stroke in the baseline
- In patients with/ without prior TIA in the baseline
- In patients with/without prior systemic embolism at baseline
- In patients with/without prior gastrointestinal bleeding at baseline
- In patients with/without prior intracranial bleeding at baseline
- In patients with/without diabetes in the baseline

Depending on sample size, subgroup analyses for the primary and the composite endpoint may be repeated in some of the above subgroups with appropriate re-matching.

